2.3 Randomization and Masking

Children meeting inclusion criteria will be enrolled by a local health agent after consent from guardian is obtained. At enrollment, children will be assigned a study identification number. Enrolled children will then undergo a baseline assessment. The baseline assessment includes data collection on demographics and socioeconomic status as well as anthropometric assessments. After completion of the baseline assessment, children will be randomized to receive either (1) a single dose of directly observed oral azithromycin plus a 5-day course of placebo or (2) a 5-day course of oral amoxicillin.

The randomization sequence will be generated by the UCSF investigators using R (R Foundation for Statistical Programming, Vienna, Austria). Children will be randomized in a 1:1

fashion to a single dose of azithromycin with short course of placebo or a short course of oral amoxicillin. The randomization sequence will be linked to the study identification numbers and kept separately so outcomes assessors are not aware of the treatment allocation. When a child has been enrolled and has completed the baseline assessments, a different health agent will determine the allocation and will administer study medication indicated as described in Section 4.

To keep the allocation concealed, only the study nurse administering treatment will have access to the randomization allocations. The study nurse will treat the child in a private room without the outcome assessor present. For each enrolled child, the treatment administered will be recorded on the mobile data collection app not accessible by the outcome assessor.

Given the nature of the intervention, the personnel administering treatment will not be masked to treatment assignment. Participants will be masked to treatment assignment, as parents of the children given azithromycin will receive a placebo syrup to give their child. Outcome assessors will be masked to treatment assignment; this will be accomplished by assigning one health agent to administer treatment and a separate masked health agent to perform outcome assessments, including anthropometry, and vital status updates.

2.4 Interventions

Children will be randomized to receive a single directly observed dose of oral azithromycin plus placebo or a short course of oral amoxicillin. Azithromycin and the first dose of amoxicillin will be administered at the time of enrollment (see Section 4 for study medication details). Except for antibiotics, all children will receive standard outpatient treatment for uncomplicated SAM per the guidelines of the government of Nigeria, which includes RUTF (Plumpy'Nut, Nutriset) as follows:

Weight (in kg)	RUTF (paste)	
	packets per day	packets per week
3.5 - 3.9	1 1/2	11
4 - 5.4	2	14
5.5 - 6.9	2 1/2	18
7.0 - 8.4	3	21
8.5 - 9.4	3 1/2	25
9.5 - 10.4	4	28
10.5 - 11.9	4 1/2	32
> = 12	5	35

Standard treatment also includes:

- Weekly appetite test, MUAC, and weight measurement
- Weekly clinical examination
- Weekly health and nutrition education
- Weekly evaluation of RUTF consumption
- Home visit if needed
- Monthly height / length measurement

2.5 Outcomes

Primary Outcome

Weight gain over 8 weeks (Specific Aim 1). Weight will be measured at all follow-up time points and weight gain will be defined as grams per kilogram per day (g/kg/day).

Secondary Outcomes

Nutritional recovery by 8 weeks (Specific Aim 2). Nutritional recovery will be defined as a child having WHZ \geq -2 on two consecutive visits and no acute complication or edema for the past 7

[figure not shown]
days AND / OR MUAC of $\geq 125\text{mm}$ on 2 consecutive visits and no acute complication or edema for the past 7 days. The criteria chosen to define the recovery will be the same one we used to admit the child into the program as defined in the national guidelines:

Criteria of admission	Criteria of discharge
MUAC < 11.5cm	MUAC > 12.5cm (for 2 consecutive weeks) Sustained weight gain Clinically well
Bilateral oedema	MUAC > 12.5cm No oedema for 2 consecutive visits Clinically well
WHZ < -3 SD	MUAC > 12.5cm AND WHZ >-2 for 2 consecutive visits Clinically well

- **Weight gain over 12 weeks.** Weight will be measured at all follow-up time points and at 12 weeks after admission to the program. Weight gain will be defined as grams per kilogram per day (g/kg/day).
- **Time to recovery.** Time from enrollment to nutritional recovery (defined above) will be calculated in days by subtracting the date of enrollment from the date of nutritional recovery.
- **Nonresponse at 8 weeks.** Nonresponse will be documented if a child does not meet the criteria for nutritional recovery at 8 weeks.
- **Transfer to inpatient care.** The occurrence, date, and reason for transfer from outpatient to inpatient treatment will be recorded.
- **Mortality by 8 weeks.** Vital status will be assessed at all follow-up time points and mortality will be defined as death during the study period. Date of death will be recorded.
- **Mortality by 12 weeks.** Vital status will be assessed at all follow-up time points and mortality will be defined as death during the study period. Date of death will be recorded.
- **Clinical signs of infection.** At all follow-up time points, clinical signs of infection will be recorded, including care-giver reported experience of fever, diarrhea, vomiting, and respiratory infection/cough and clinical diagnoses made at by site personnel
- **Adverse events.** Adverse events will be reported at all follow-up time points
- **HAZ.** Height or length will be measured monthly and height-for-age z-scores will be calculated.
- **MUAC.** Mid-upper arm circumference will be measured at all follow-up time points.
- **WAZ.** Weight will be measured at all follow-up time points and weight-for-age z-scores will be calculated.
- **WHZ.** Weight and height, assessed at all follow-up time points, will be used to calculate weight-for-height z-scores.
- **Malaria.** Rapid diagnostic tests for malaria will be conducted at baseline and week 8 to determine malaria infection status.

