1.2 Design Overview

We propose a randomized controlled trial to examine the effect of the adjunctive administration of azithromycin compared to amoxicillin in the treatment of children aged 6-59 months with uncomplicated SAM. We will randomize children presenting to nutritional programs in Gombe State, Nigeria to a single dose of oral azithromycin or a short course of oral amoxicillin upon admission into the program and follow them at each weekly clinic follow-up visit up to 8 weeks following admission. All enrolled children will receive non-antibiotic routine care for uncomplicated SAM as stated by the Nigeria guidelines, which includes ready-to-use therapeutic food (RUTF). Anthropometric and vital status data will be collected during follow-up. Weight gain and nutritional recovery over the 8-week study period will be compared by study arm.

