2.6 Participant Timeline

Figure 1. Participant Timeline and Flow

- Clinical examination outcomes (diagnoses, treatments)

Monthly:

- Anthropometry (Height, length)

Week 8:

- Malaria RDT

Week 12:

- Anthropometry (height, weight, MUAC)
- Vital Status

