3.2 Anthropometry

Anthropometric assessments (height or length, weight, and MUAC) will be recorded by health agents at baseline, weekly until recovery, week 8 and week 12.

Supplies

- Mobile data collection device & accessories
- Height and length tapes
- Digital scale
- MUAC strips
- Chucks and alcohol swabs
- Pens and sharpie markers
- Trash bags
- Extra set of AA batteries (6)

[figure not shown]
Anthropometry Team

Two health agents will conduct anthropometry: 1) examiner and 2) recorder. The examiner will conduct the anthropometric assessments, and the recorder will enter data into the mobile application.

Measuring Length (National operational guidelines for CMAM Nigeria)

How to measure LENGTH (when lying down) If the child is less than 87cm, he/she should be measured lying down.

1. One person holds the child's head, making sure the child's head is touching the back of the board. The child's eyes should be looking straight up.
2. The other person holds down the child's knees, pressing the sliding wood piece against the child's heels and soles of the feet.
3. Align the child with the board
4. Child's arms should be lying alongside his/her body, and if necessary, the mother can hold the arms down
5. The person holding the feet reads the measurement.

[figure not shown]

Measuring Height (National operational guidelines for CMAM Nigeria)

How to measure HEIGHT (when standing) If the child is more than 87cm, he/she should be measured standing.

1. Place the child's feet flat and together in the centre of and against the back and base of the wall.

2. One person places their right hand just above the child's ankles on the shins, left hand on the child's knees and push against the wall. Make sure the child's legs are straight and the heels and calves are against the wall
3. Tell the child to look straight ahead making sure the child's line of sight is level with the ground.
4. The second person should place their open left hand under the child's chin. Do not cover the child's mouth or ears. Make sure the shoulders are level, the hands are at the child's side, and the head, shoulder blades, and buttocks are against the wall.
5. When the child's position is correct, person holding the legs reads (at eye level) and call out the measurement to the nearest 0.1 cm.

Measuring Weight

Tempered glass digital standing scales will be used to weigh infants and children to the nearest 0.1 kg.

For infants and children who cannot stand:

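### Length/height is scheduled monthly in some sections and at every visit in others, so recovery judged on WHZ at two consecutive weekly visits may lack a measured height

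*Combined protocol and SAP*

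**What the plan says.** All references are to the combined protocol and SAP.

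Two places schedule length/height at every visit:
- Section 2.5, WHZ outcome: "Weight and height, assessed at all follow-up time points, will be used to calculate weight-for-height z-scores".
- Section 3.2: "Anthropometric assessments (height or length, weight, and MUAC) will be recorded by health agents at baseline, weekly until recovery, week 8 and week 12".

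Three places schedule it monthly:
- Section 2.5, HAZ outcome: "Height or length will be measured monthly and height-for-age z-scores will be calculated".
- Section 2.6, under the monthly heading of the timeline: "Anthropometry (Height, length".
- Section 2.4, standard care: "Monthly height / length measurement". The weekly measurements in the same list are "Weekly appetite test, MUAC, and weight measurement", with no height.

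Section 2.5 defines recovery on the WHZ route as WHZ of at least -2 "on two consecutive visits and no acute complication or edema for the past 7" days. Section 1.2 sets the visit interval: the investigators will "follow them at each weekly clinic follow-up visit up to 8 weeks following admission". No section says which height enters WHZ at a visit where none was taken.

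**The concern.** WHZ needs a weight and a height. A site working from the HAZ outcome and the timeline would have a weight every week but a height only once a month. It could then leave WHZ undetermined at most visits, or pair the current weight with an old height. A site working from section 3.2 would have both measurements each week. Each site would be following the protocol, yet they could classify the same child differently or date that child's recovery differently.

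The error from an old height has a known direction. A growing child is taller than the last recorded height, so the weight is compared with too low a reference and WHZ comes out too high. Recovery can then be declared early.

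The outcomes at stake are recovery by 8 weeks (Specific Aim 2, which has its own power statement in section 9.1), time to recovery, nonresponse and WHZ itself. Section 2 also ends routine weekly follow-up at recovery. An early call therefore removes the next weekly visits at which it might have been corrected, leaving the week 8 and week 12 visits.

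**Working it through.** **1. The plan's own figure for the affected outcome.** Section 9.1 claims 80% power for a 12-point difference in recovery from 36%, with 540 evaluable children (270 per arm) and alpha 0.05, taken as two-sided.
- Standard error under the null: sqrt(2 × 0.42 × 0.58 / 270) = 0.0425.
- Standard error under the alternative: sqrt((0.36 × 0.64 + 0.48 × 0.52) / 270) = 0.0422.
- z = (0.12 − 1.96 × 0.0425) / 0.0422 = 0.87, so power is 0.808.

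The figure reproduces, and nothing below changes it. The issue is whether the outcome can be determined as defined.

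**2. Visit count.** There are eight weekly follow-up visits (weeks 1 to 8), giving seven consecutive pairs (1–2 to 7–8). The document does not say which weeks count as monthly; weeks 4 and 8, in addition to baseline, are assumed.
- Monthly schedule: weeks 1, 2, 3, 5, 6 and 7 have no same-day height, which is 6 of 8 visits (75%). Pairs with a height at both visits: 0 of 7.
- Every-visit schedule: 0 of 8 visits lack a height. Pairs with a height at both visits: 7 of 7.

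**3. Effect of carrying a height forward.** Assumptions from outside the document: linear growth of 0.5 to 1.2 cm per 28 days, and 0.2 to 0.35 WHZ units per cm.

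Overstatement = (z per cm) × (cm per 28 days) × (days since height) / 28.
- 1 week old: 0.2 × 0.5 × 7/28 = 0.025, to 0.35 × 1.2 × 7/28 = 0.105.
- 2 weeks old: 0.05 to 0.21.
- 3 weeks old: 0.075 to 0.315.

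**4. Conversion to time.** Section 9.1 gives a gain of 2.6 g/kg/day. Further assumptions: a 6.2 kg child, and 0.5 to 0.7 kg per WHZ unit.
- Weekly gain = 2.6 × 6.2 × 7 = 113 g.
- In WHZ units: 0.113 / 0.7 = 0.16, to 0.113 / 0.5 = 0.23 per week.
- A three-week-old height is worth 0.075 / 0.23 = 0.3 weeks, to 0.315 / 0.16 = 2.0 weeks.

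The divisor is weight-driven gain only. Subtracting the pull of linear growth on true WHZ (0.025 to 0.105 per week, from step 3) would shrink it and lengthen the shift, so 2 weeks illustrates the size and is not an upper bound.

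**The case against.** **Part of the conflict is softer than a count of three against two suggests.** Section 2.4 describes programme care, and a study may measure more often than standard care without contradicting it. The readable text of the timeline in section 2.6 is incomplete. Both points stand. They do not remove the conflict: the HAZ outcome is study text, sits in the same section as the WHZ outcome, and disagrees with it and with section 3.2.

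**The effect is confined.** In the discharge table of section 2.5, children admitted on MUAC or oedema are never judged on WHZ, and children admitted on WHZ must also exceed a MUAC of 12.5 cm. On that table, an old height matters only for WHZ admissions who have already met the MUAC criterion. This stands. The share of such children is not stated, and community screening (section 2.2) uses MUAC.

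**A reader might infer that one arm is favoured, for instance if its children grow taller faster.** The documents do not support this. Section 2.3 randomizes individual children 1:1 and masks outcome assessors, both arms share whatever schedule a site follows, and nothing indicates different linear growth by arm. Differences in site practice add noise and misclassification; they do not in themselves bias the comparison.

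**A reader might also infer that the monthly schedule merely delays confirmation to week 8, using weeks 4 and 8 as the two visits.** With weekly visits, weeks 4 and 8 are not consecutive, so on measured heights no qualifying pair exists at all.

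**Conclusion.** The concern holds as an internal inconsistency in current text, together with a missing rule on which height enters WHZ. On the monthly reading, part of the Aim 2 outcome cannot be determined from measured heights as it is defined. The count of 6 of 8 visits and 0 of 7 pairs rests on monthly meaning weeks 4 and 8.

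The size of the carried-forward error, about 0.08 to 0.32 WHZ or roughly 0.3 to 2 weeks for a three-week-old height, rests on growth and conversion figures that are not in the document. It shows that the error could matter for an outcome counted in days; it is not an estimate for this trial.

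The harm is misclassified or misdated recovery, and inconsistency between sites, among children whose recovery depends on WHZ. Recovery by 8 weeks, time to recovery, nonresponse and WHZ are touched. A reader might take this as a threat to the main result, but the primary outcome is weight gain in g/kg/day and uses no height. The point should be corrected, but it does not undermine the trial's primary comparison.

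**What to change.** For study outcome measurement, bring the HAZ outcome in section 2.5 and the timeline in section 2.6 into line with the WHZ outcome and section 3.2: length or height recorded at each weekly study visit up to recovery, and at weeks 8 and 12.

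At minimum, take a same-day height at the first visit where WHZ meets the threshold and again at the confirming visit, and compute the WHZ used for the recovery outcome only from same-day heights. State in section 2.5 which height enters WHZ at each visit.

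The standard-care list in section 2.4 and the programme's discharge rules need not change. Section 3.2 already prescribes weekly height by a two-person team, so no new procedure is introduced. Where sites already measure weekly, this is only an edit; where they measure monthly, the cost is a slightly longer visit. The sample size is unaffected.

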2.6 Participant Timeline

Figure 1. Participant Timeline and Flow

- Clinical examination outcomes (diagnoses, treatments)

Monthly:

- Anthropometry (Height, length)

Week 8:

- Malaria RDT

Week 12:

- Anthropometry (height, weight, MUAC)
- Vital Status

2.7 Study Team, Roles, Responsibilities

- **Investigators (UCSF).** The UCSF investigators will be responsible for the overall study design and implementation, data management and monitoring, data analysis, and dissemination of results in collaboration with Taimaka investigators. The UCSF investigators will design and implement trainings for study procedures and maintain weekly communication with local Nigerian study staff.
- **Investigators (Taimaka Project).** The Taimaka investigators will be responsible for overall study design, implementation, data management and monitoring, data analysis, and dissemination of results in collaboration with UCSF investigators. The Taimaka investigators will oversee all local study activities, including training and regular supervision and monitoring of local study staff.
- **Medical Monitor.** The Medical Monitor will provide clinical oversight for the enrolled children. Study Team Members will report serious adverse events to the Medical Monitor within 24 hours of occurrence, and the Medical Monitor will determine whether or not the event is likely to be related to the study drug. In addition, the Medical Monitor will provide clinical guidance for the adverse event as needed.
- **Data and Safety Monitoring Committee.** The Data and Safety Monitoring Committee will provide independent oversight of data quality and patient safety during the course of the trial. See Section 8 for details.
- **Study Team Members (Taimaka project).** Study Team will be responsible for implementation of all study procedures as described in this protocol, including recruitment, consent, enrollment and randomization, drug administration, and collection of all study data.
 - **Health agent administering treatment.** A health agent at each OTP center will be trained to determine the randomization allocation of enrolled children and to administer azithromycin if indicated.
 - **Outcome Assessor.** One health agent will be an outcome assessor for each site and will be trained to manage consent, enrollment, and collection of all study data, including outcome assessments.

3. PROCEDURES

3.1 Training

All members of the OTP nutrition team will participate in multi-day training which will include a section on the particulars of study protocol. In addition, study nurses (study officers) who will be administering the treatment will receive a separate initial training. Study officers must achieve a score of >80% on the training quiz in order to participate in the study. Training will include a mix of lecture and practice. Taimaka's OTP manager will supervise the adherence to study protocol by the nutrition team and the study officer and regularly check up on their understanding and memory of study protocols.

3.2 Anthropometry

Anthropometric assessments (height or length, weight, and MUAC) will be recorded by health agents at baseline, weekly until recovery, week 8 and week 12.

Supplies

- Mobile data collection device & accessories
- Height and length tapes
- Digital scale
- MUAC strips
- Chucks and alcohol swabs
- Pens and sharpie markers
- Trash bags
- Extra set of AA batteries (6)

[figure not shown]
Anthropometry Team

Two health agents will conduct anthropometry: 1) examiner and 2) recorder. The examiner will conduct the anthropometric assessments, and the recorder will enter data into the mobile application.

Measuring Length (National operational guidelines for CMAM Nigeria)

How to measure LENGTH (when lying down) If the child is less than 87cm, he/she should be measured lying down.

1. One person holds the child's head, making sure the child's head is touching the back of the board. The child's eyes should be looking straight up.
2. The other person holds down the child's knees, pressing the sliding wood piece against the child's heels and soles of the feet.
3. Align the child with the board
4. Child's arms should be lying alongside his/her body, and if necessary, the mother can hold the arms down
5. The person holding the feet reads the measurement.

[figure not shown]

Measuring Height (National operational guidelines for CMAM Nigeria)

How to measure HEIGHT (when standing) If the child is more than 87cm, he/she should be measured standing.

1. Place the child's feet flat and together in the centre of and against the back and base of the wall.

2. One person places their right hand just above the child's ankles on the shins, left hand on the child's knees and push against the wall. Make sure the child's legs are straight and the heels and calves are against the wall
3. Tell the child to look straight ahead making sure the child's line of sight is level with the ground.
4. The second person should place their open left hand under the child's chin. Do not cover the child's mouth or ears. Make sure the shoulders are level, the hands are at the child's side, and the head, shoulder blades, and buttocks are against the wall.
5. When the child's position is correct, person holding the legs reads (at eye level) and call out the measurement to the nearest 0.1 cm.

Measuring Weight

Tempered glass digital standing scales will be used to weigh infants and children to the nearest 0.1 kg.

For infants and children who cannot stand:

1. Before weighing the child, take all his/ her clothes off
2. Zero the scale
3. Ask the mother to step onto the scale and record her weight in the mobile app.
4. Place the child into her arms.
5. Record the total weight in kg to the nearest 0.1 kg and enter into the mobile app. The app will calculate the weight of the child.
6. Do not hold the scale when reading the weight

[figure not shown]
For children who can stand:

7. Before weighing the child, take all his/ her clothes off
8. Zero the scale
9. Ask the child to stand on the scale
10. Make sure the child is not holding onto anything
11. Record the weight in kg to the nearest 0.1 kg in the mobile app
12. Do not hold the scale when reading the weight

Measuring Mid-Upper Arm Circumference (National operational guidelines for CMAM Nigeria)

The child's MUAC will be measured **three times**. MUAC measurements will be taken at the midpoint of the **left** arm between the tip of the shoulder and the tip of the elbow using non-stretch MUAC tapes.

- 1- Find the midpoint. Ask the patient to stand, or for a small child, have the caregiver hold the child, with the patient's left arm bent at a 90-degree angle. Find the bone that forms the tip of the shoulder (acromion process), and place the zero point of the MUAC measure there (it is usually the middle of the window). Extend the MUAC tape down to the tip of the elbow (olecranon process). Read the length in mm of this distance between shoulder and elbow; then divide this number in half to find the mid-point (or fold the tape in half between the zero and the elbow point). Mark the mid-point in pen on the patient's arm.
- 2- Position the patient to read the MUAC. Have the patient stand or sit with the left arm hanging loosely by the side of the body. Muscles should not be flexed at all.
- 3- Measure the MUAC. Place the MUAC tape around the left arm at the midpoint mark. It should fit snugly around without constricting the arm. Read the measurement from the window of the tape. Take the measurement to the nearest 0.1cm.

Source: How to Weigh and Measure Children: Assessing the Nutritional Status of Young Children, United Nations, 1986.

